1 BACKGROUND

In 2014, with a news release, the WHO revealed that in 2012 around 3.7 million people had died prematurely in the world as a result of exposure to ambient air pollution. These deaths were attributed to specific diseases such as heart disease, stroke, chronic obstructive pulmonary disease (COPD), lung cancer and acute respiratory infections in children (1). In this context, it has been recommended to inform the general population, and in particular individuals who are more susceptible to experience symptoms (e.g. due to lung or heart problems), with the aim of raising awareness about air pollution and its health impact, and to provide advice on how to reduce exposure (2). However, the evidence shows that adherence to air quality advice to modify behaviours during pollution episodes is often suboptimal ([name] et al., unpublished systematic review(3),(4)), and that the traditional strategy of simply informing people about high pollution episodes is not effective (5).

The aim of this project is to improve the behavioural impact of air quality alerts. In particular, I have conducted a systematic literature review of the predictors of adherence to air quality alerts. This review has informed the development of specific communication strategies, which after being piloted, will be used with the users of an existing air alert smartphone App developed by the KCL ERG group. Implications of this study include the potential to reduce the health burden of air pollution, through the development of more effective communication strategies provided via existent air quality alert systems.

1.1. Systematic literature review: Psychosocial predictors of adherence and non-adherence to health advice provided through air quality information services

The aim of this systematic review was to understand to what extent the general public adopt protective behaviours in response to hearing or reading air quality warning systems and the health advice accompanying them, and to identify the demographic and psychosocial factors associated with adherence and non-adherence to the received health advice.

1.1.1. Methodology

The present review is conducted and reported in accordance with the Preferred Reporting Items for Systematic reviews and Meta-Analysis (PRISMA) guidelines (6), using systematic methods to identify and select studies, and assess their risk of bias.

1.1.2. Search Strategy

We searched electronic databases such as Web of Science Core Collection, OVID (Global Health 1973 to 2016 week 18), PsycINFO (1806 to May 2016), Social Policy and Practice (2016), Embase (1947 to May 2016), Ovid MEDLINE(R) (1946 to present), Science Direct, Scopus, Pubmed, CINAHL in August 2016. In addition, OpenGrey.eu, EThos, and google were used to identify relevant unpublished studies and reports (e.g. governmental reports). No date limit or study type limit were applied, however papers published only as abstracts were excluded. We only searched for literature written in English. The search strategy combined terms related to air quality alerts (i.e. 'air quality alert', 'air quality index', 'air quality advisories', 'smog alert'), and adherent and protective behaviours (i.e. 'adherence', 'compliance', 'health behaviour', 'risk reduction', 'public response'). The search was conducted to make sure that both the general public and vulnerable population (e.g. asthmatics) were included. Additional articles were included through manually screening reference lists of relevant articles and reports.

1.1.3. Inclusion criteria

The inclusion criteria were based on the Participants, Interventions, Outcomes, and Setting -PI(C)OS - approach in the PRISMA guidelines. Studies were included if they met the following criteria:

- i. Participants: people who read or heard of air quality reports, alerts, indices or other sources of health information related to air quality (e.g. users of air quality warning systems, people familiar with air quality forecasts). Participants could be drawn from the general public, patient groups or specific occupational groups.
- ii. Interventions: exposure to information about air quality and/or health advice associated with air quality levels, including information related to actual and/or hypothetical levels of air pollution.
- iii. Outcomes/Predictors: Actual and/or intended adherence/ behaviour change in response to air quality information,
AND/OR
Predictors of, and/or self-reported reasons for adherence or non-adherence to health advice associated with air quality information.
- iv. Study reporting: All study designs, aside from those published only as editorials or abstracts, were included. Studies were excluded if they met the following criteria:
 - v. Were based on the assumption that the respondents were aware of air quality alerts Involved a population only assumed to be aware of air quality information services during alert days (i.e. every time an alert was issued in a specific area), but did not collect evidence of this;
 - vi. Analysed behaviour change in response to air quality as driven by people’s own perception of air quality, without the involvement of any official information;
 - vii. Analysed only information seeking behaviour and/or frequency of access of air quality information services, without investigating behavioural changes in response to this activity;
 - viii. Investigated pro-environmental behaviours only.

[figure not shown]

Fig. 1. PRISMA flow diagram with literature search (Last search 9th Aug 2016)

1.1.4. Studies characteristics

Design

The majority of the studies were conducted in the USA (7–16), whereas five were conducted in the UK (17–21), four in Canada (22–25), one in Hong Kong (26), and one in Denmark (27). Data collection covers the period from 1982 to 2016. The vast majority of the included studies were cross-sectional surveys (7,10–18,20,21,24–27). Although there was only one qualitative study (23), other studies collected some qualitative data through asking people to report the reasons for adherence and/or non-adherence (12,17,24,25). The studies included samples of general public, service users of air alert systems, asthmatic patients and people with other respiratory and/or heart condition, elderly, people who spend most of their time working in busy streets, communities involved in wildfire events, parents of healthy and parents of asthmatic children, and health care professionals. The majority of the studies focused on air quality forecasts and alerts with associated health advice, one study used a web-based asthma action plan smartphone application, and one study investigated responses to emergency risk communications during a local wildfire episode. Air quality information was provided through different public media, with almost half of the studies assessing actual adherence with messages received also through personal channels such as telephone messages, emails notifications, and smart phone applications.

Outcomes (adherence and predictors)

Adherence to health advice associated to air quality information was investigated via non-validated self-report questionnaires or interviews in all but one study (19), which used objective emergency department attendances. The majority of the studies investigated actual adherence, with only three studies investigating intended adherence (8,9,20), and one study assessing both actual and intended behaviour (27).

1.1.5. Results: adherence rates

Actual behaviour: reducing/rescheduling outdoor activities

In the studies investigating actual adherence to the health advice to avoid, reduce or reschedule outdoor activities during poor air quality, overall adherence rates ranged from 9.7% (12) to 70.7% (27), with median adherence rates of 36% (11).

Actual behaviour: additional protective behaviours

In the studies investigating a wider range of actual protective behaviours, going beyond the decision to simply reduce or reschedule outdoor activities, overall adherence (including also behaviours performed less than monthly during moderate or high pollution episodes) ranged from 17.7% (26) to 98.1% (13), with median adherence rates of 42% (18). The most common responses reported by all study participants included: avoiding busy or polluted road (with adherence rates ranging from about 10% to 52.5% (17,18,21), spending more time indoors (ranging from about 30% to 58.7% (13,18,21), adjusting or rescheduling travels or other outdoor activities (41.4%), changing means of travel (38.6%)(21), and avoiding strenuous exercise or other outdoor activities (ranging from 17.4% to 88.4% (13,17,18,22,26). Other behaviours included taking a reliever medication (ranging between 30.5% and 50% (17,18), taking a preventative medication (30.5%-38.5% (17)), getting advice from GP (about 1% (18,26)), and wearing a mask (6.4% to 8.1% (13,26)).

Intended behaviour

These studies showed an overall intention to adhere ranging from 36.4% (20) to about 81.8% (27) (the latter refers to a group of respondents with severe lung disease).

1.1.6. Psychosocial predictors of adherence and non-adherence

Table 1 categorises within the COM-B framework the main factors affecting adherence to health advice provided with air quality information services, as found in our systematic review. Socio-demographic factors are not reported here as not modifiable and therefore not relevant to this project. Full details on the predictors reported in [name] et al. systematic review (submitted for publication).

Table 1. Factors influencing adherence to health advice provided in association with air quality information services within the COM-B models.

CAPABILITY	MOTIVATION	OPPORTUNITY

Psychological
 
 Knowing where to check AQHI (Air Quality Health Index) numbers (24) Understanding the air quality indices/ health messages (17,23,24) Confusion between different indices (23) Awareness of media alerts (28) Information seeking behaviour (11) 	
Reflective
 
Health messages able to reduce both concern about, and perceived susceptibility to, air pollution (9)
 
Experiencing symptoms ascribed to air pollution (beliefs about the illness & threat) (21,27)
 
Beliefs that smog can have negative health effects (beliefs about the health threat) (7,21)
 
Beliefs that something can be done to reduce smog (outcome expectancies) (7)
 
Perceived benefits of AQI (Air Quality Index) adoption (beliefs about the recommendation) (17,23,24)
 
Perception of lack of necessity of AQI adoption (beliefs about the recommendation) (24,25)
 
Lack of message relevance (23,25)
 
Self-efficacy/locus of control (24,25)
	
Physical
 
 Wearable device option/ smartphone applications (19,21,23) Exposure to visible air pollution (13,15)
	
Automatic
 
Depression (13)
 
Reliance on sensory cues (12,17,23,24)
	
Social
 
 Professional health care network promotion/GP advice (13,23,28) Neighbourhood scale focus (23) Local media reporting (23,24) Use of different sources of information (21) Necessity to continue with everyday life/ Lack of time (17,23,24)

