4 RESEARCH QUESTION/AIM(S)

The purpose of the present study is to test whether theory and evidence-based alternative communication formats, targeting message specificity and previously identified psychosocial predictors of adherence, could improve the behavioural impact of existing alert systems, compared to the official messages sent in association with the UK AQIs.

Research questions

Primary questions:

1) What is the main effect of using behaviourally enhanced messages, compared to the currently used DAQI messages, to present the health advice associated with air quality notifications for a hypothetical high air pollution scenario on adherence intentions?

Prediction:

A) The behaviourally enhanced messages will lead to stronger intentions to adhere to recommendations.

2) What is the main effect of using a behaviourally enhanced message, compared to the currently used DAQI messages, to present the health advice associated with air quality notifications on actual behaviour changes at four weeks?

Prediction:

A) The enhanced messages will lead to greater behaviour changes.

3) In case of a real alert being issued during the study period, how do the different messages affect actual behaviour change?

Prediction:

A) The enhanced messages will lead to greater behaviour change.

Secondary questions:

4) If there is a format effect, which variables mediate the relationship between the information format and behaviour change?

5) Which factors are associated with greater behaviour change across all groups?

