Medication adherence intentions ^a	If you have lung problems: - I intend to use my preventer inhaler daily - I intend to carry my reliever inhaler with me
Other intentions (not advised behaviours) ^a	- I will wear a mask as a protection from air pollution - I intend to reduce length or level of my physical exercise indoors

Notes: ^a Measured on 9-point scales, where 1=strongly disagree to 9=strongly agree; ^b From 1 Not at all to 9 all of the time; ^c Possible answers: yes, no, not sure; ^d From 1 Not at all, to 7 more than 150 minutes; ^e Possible answers: Low, Moderate, High, Very High, Not sure, I did not receive any alert; ^f From 1=not at all likely to 9=extremely likely; ^g on a 5-point scale; ^h 1= not clear at all to 9= extremely clear. Demographic data will be collected for all the participants in the first questionnaire.

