6. STATISTICAL ANALYSES

6.1 Quantitative data

ANCOVAs will be performed for all the intentions measures in relation to the high air pollution hypothetical scenario, adjusting for baseline measures collected about one month earlier (target population and intervention/control group entered as fixed factors). Both main and interaction effects will be tested. ANCOVAs will also be performed for the actual behaviour change at 4 weeks (with the intervention/control group entered as fixed factor). These latter analyses will also be ran in the subgroups of healthy and at-risk participants. Chi square tests will be performed to analyse differences in proportion of self-reported actual behaviour change between groups, in relation to a real moderate air pollution episode. A two-way MANOVA (1000 bootstraps) will test whether there are differences between groups (both main effects and interactions) in perceived susceptibility, worry, severity, perceived response efficacy, perception of time, self-efficacy, trust, clarity, credibility and perceived informed choice measures. Multiple linear regressions will be used to assess the associations between main predictor variables and self-reported behaviour change at 4 weeks. Mediations effects of predictor variables on significant behavioural changes will be tested using PROCESS macro (38).

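### Section 6.1 names no baseline covariates for the question 5 regressions or the question 4 mediation, so shared causes of belief and behaviour may be reported as predictors or mediators

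*Combined protocol and SAP*

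**What the plan says.** Section 4 lists two secondary questions. Question 4 asks "If there is a format effect, which variables mediate the relationship between the information format and behaviour change". Question 5 asks "Which factors are associated with greater behaviour change across all groups".

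Section 6.1 gives each one sentence. For question 5: "Multiple linear regressions will be used to assess the associations between main predictor variables and self-reported behaviour change at 4 weeks". For question 4: "Mediations effects of predictor variables on significant behavioural changes will be tested using PROCESS macro". The set of predictors is not defined, and neither sentence names a covariate.

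Elsewhere in 6.1, target population is a fixed factor in the intentions ANCOVAs, and the 4-week behaviour ANCOVAs are repeated in the healthy and at-risk subgroups. Neither provision is extended to the regressions or the mediation.

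The data for adjustment exist. The notes to Table 4 say "Demographic data will be collected for all the participants in the first questionnaire", and section 8.7 mentions age and gender among the sample descriptors. Health condition is asked at entry (5.4.2). The first questionnaire also asks about symptoms ever caused by air pollution and about protective action in the previous four weeks. The belief items appear only in the final questionnaire, next to the 4-week behaviour item.

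In the Background, section 1.1.6 introduces Table 1 with the remark "Socio-demographic factors are not reported here as not modifiable and therefore not relevant to this project".

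**The concern.** Randomising the message format protects the effect of format on beliefs and the effect of format on behaviour. It does not protect the association between a belief and behaviour. That association is what question 5 estimates, and it is also the second path of the mediation in question 4. Anything present at baseline that raises both a belief and protective action will make the belief look like a predictor, or a mediator, even if changing the belief would do nothing.

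The plan itself gives reasons to expect such causes. The two-way MANOVA looks for group differences in susceptibility, worry, severity and efficacy; in this design one of the two factors is target population. Section 5.4.1 says that CityAir normally sends moderate alerts only to at-risk users, so health status also shapes alert history. Table 1 lists symptoms ascribed to pollution as an influence on adherence and classes them under beliefs about illness and threat.

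At stake is the advice drawn from questions 4 and 5: which beliefs explain the effect of the messages, and which beliefs later messages should target.

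**Working it through.** The plan gives no figure on this point to reproduce. The check asks how often an unadjusted analysis would find a belief effect that does not exist.

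**Inputs**
- Completers: the target in 5.3 is 240 after 20% inflation, so 240 / 1.2 = 200. If 20% of 240 are lost, 240 × 0.8 = 192.
- Level 0.05 (5.3). Two-sided tests and equal allocation are assumptions.
- One standardised shared cause C with correlation r to both belief M and behaviour Y. The documents do not give r, so a range is shown.
- Format shifts the belief by 0.4 SD (assumed), with 0.2 SD as an alternative. The only message-effect figure in the plan is the persuasion correlation of .10 in section 2, which corresponds to d = 2 × 0.10 / √(1 − 0.01) = 0.20.

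**Question 5: false predictors.** Let M = 0.4 × arm + rC + error and Y = rC + error, with no effect of M on Y. Within arm, M and Y then correlate at r × r = r². The test statistic is centred near z = r²√n / √(1 − r⁴), and the rejection rate is Φ(z − 1.96) + Φ(−z − 1.96). With n = 200, √n = 14.14. The simulations used 3,000 runs per setting at n = 192.

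| r | r² | z (n = 200) | Formula | Simulated, n = 200 | Simulated, n = 192 | n = 192, C adjusted |
|---|---|---|---|---|---|---|
| 0.1 | 0.01 | 0.14 | 5% | about 5% | 4.9% | 4.9% |
| 0.2 | 0.04 | 0.57 | 9% | 8–9% | 9.0% | 5.3% |
| 0.3 | 0.09 | 1.28 | 25% | 24% | 23% | 5.6% |
| 0.4 | 0.16 | 2.29 | 63% | 63% | 60% | 5.1% |

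Formula and simulation agree. The bias is negligible at r = 0.1 and serious from about r = 0.3. Adjusting for C restores the nominal level.

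**Arm in the question 5 model.** If format moves both belief and behaviour by 0.4 SD and arm is left out of a pooled regression, arm is itself a shared cause. It adds a covariance of 0.4 × 0.4 × 0.25 = 0.04 against a variance of 1.04, a correlation of 0.04 / 1.04 = 0.038. That is about what a shared cause at r = 0.2 produces.

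**Question 4: false mediation.** The plan tests mediation only for significant behaviour changes, so that condition must be applied.
- *No format effect on behaviour.* The condition is met in about 5% of trials. Without it, joint-significance testing at n = 200 declares false mediation in 6%, 21%, 50% and 78% at r = 0.2, 0.3, 0.4 and 0.5. With it, the rates are 0.1%, 1.2%, 2.1% and 4.0%. As a rough check at r = 0.4, 0.05 × 50% = 2.5%.
- *A format effect of 0.4 SD by another route (assumed).* This equals f = 0.2, for which power at 200 is 0.80, so the condition is usually met. False mediation is then about 16% at r = 0.3 and 41% at r = 0.4 (rough check: 0.80 × 21% = 17% and 0.80 × 50% = 40%). If the belief shift is 0.2 SD, the figures are about 6% and 16%.

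**The case against.** Several stronger readings are tempting, and the documents do not support them.

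A reader might take the remark in 1.1.6 as a decision to keep socio-demographic and health factors out of the analysis. It is not. It sits in the Background, explains what Table 1 leaves out, and does not mention health factors. Health status is a design factor (5.1), determines message content (5.4.1) and is used in other analyses in 6.1. Symptoms are listed in Table 1 itself.

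A reader might also infer that no adjustment will be made. The text is silent rather than exclusionary: the predictors are undefined, question 5 is not limited to beliefs, and a multiple regression could include age, health status or symptoms. Question 5 is also worded as association, so an unadjusted result misleads only if it is read causally. These points stand, and they limit the claim to what may be reported. They do not remove it, because a plan that fixes neither predictors nor covariates allows the unadjusted analysis and also a choice made after seeing the data.

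Third, one might quote the false-mediation rates of 50% or 78% as what the plan would produce. That ignores the significance condition; with no format effect the rates are about 4% or less.

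Finally, nothing in the documents supports an r of 0.4 between these baseline factors and both belief and behaviour, or a belief shift of 0.4 SD. Both are assumptions, which is why ranges are shown.

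**Conclusion.** The concern holds as a gap in specification. Section 6.1 names no baseline covariates for either secondary analysis, and randomisation does not cover the association that both depend on. Shared causes may therefore be presented as belief predictors or mediators.

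For question 5 the excess of false findings ranges from nil (r = 0.1) to large (63% against a nominal 5% at r = 0.4). For question 4 the problem is small if format has no effect on behaviour and becomes material only if format works by a route other than the belief tested. All these figures rest on a single shared cause, the assumed r and the assumed effect sizes. The comparisons between arms that answer the primary questions are not affected, so this is worth correcting but does not threaten the main result.

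**What to change.** In section 6.1:
- Define the predictors for question 5.
- Name age, sex, target population, symptoms ever experienced and the first-questionnaire item on previous protective behaviour as covariates. The last is the same item as the 4-week outcome.
- Enter these covariates in every question 5 regression and in both the mediator and the outcome equations in PROCESS.
- Include arm in the question 5 model.
- Describe the results of both analyses as associations.

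No change to 1.1.6 is needed.

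The cost is a few sentences and a few degrees of freedom out of about 200, with no new data. The symptom item is asked after the scenario has been read, and so after allocation; it should be treated as lifetime history. The item on previous protective behaviour is asked at the same point but refers to the preceding four weeks. The covariates will not remove unmeasured confounding. They also cannot cure the fact that beliefs and behaviour are measured together at four weeks, which leaves their order in time open. Both limits should be stated with the results.

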2 THEORETICAL FRAMEWORK

The Capability, Opportunity and Motivation (COM-B) framework, developed from existing theories of behaviour change (29), proposes that to better understand the determinants of behaviour we should consider the interactions existing between capability (C), opportunity (O) and motivation (M), where individual, group and environmental determinants are equally considered in controlling behaviours. ‘Capability’ is defined as the individual’s psychological (e.g. knowledge, understanding) and physical capacity to engage in the targeted activity. ‘Opportunity’ refers to all the external factors that make the behaviour possible or prompt it, and ‘motivation’ to the mental processes that energise and direct behaviour, including also habitual processes and emotional responses. The COM-B framework and the BCW (Behavioural Change Wheel) can be used as a guide to both identify specific determinants of target behaviours as well as identify behaviour change techniques (BCTs) aimed at modifying these determinants and in turn the relevant target behaviours (29–31). Given our focus on improving written health communications, we decided to address ‘reflective motivation’ as key determinant of adherence behaviour (see Table 1). Once identified this determinant, the next step involved an accurate

[figure not shown]

Figure 1 Behavioural Change Wheel (Michie et al. 2011)

analysis of different intervention functions aiming at addressing the targeted determinant – as reported by Michie and colleagues (29)-. We established to adopt two main functions: education, and persuasion, where education refers to increasing knowledge and understanding, persuasion refers to the use of communication to induce positive or negative feelings or stimulate action. Table 2 shows the messages we are going to use. These alternative health messages were developed based on the psychosocial factors identified in the systematic review earlier discussed.

In addition, these alternative messages were developed to provide more specific health advice. This is based on evidence showing the importance of designing health risk communications that provide specific, and clear information (32), so that sufficient information is provided to enable decisions about health protection. Specificity refers to the extent to which a message provides a detailed description of the recommended behaviour (387).

A meta-analysis of 18 studies (388) found that messages providing health recommendations with a more specific description seem to be significantly more persuasive than generic recommendations ($r=.10$, $k=18$, $N=11,105$). For instance, Leventhal and colleagues (389) found that health messages recommending tetanus vaccination that provided a more explicit description of the steps to take towards the recommended action were more persuasive than less detailed information. In addition, Frantz found that adding procedurally explicit precaution for safe use of products (e.g. ‘Open windows to vent vapours to outdoors’ or ‘Wear rubber gloves and protective glasses’) increased adherence to recommendations on how to use these products, compared to more generic instructions (e.g. ‘Use in a well-ventilated area’ or ‘Avoid contact with eyes and skin’) (391). As to why message specificity seems to be more effective, there are no conclusive explanations, however some potential mechanisms have been suggested. It is plausible that more specific descriptions of recommended behaviours make it easier for the targeted audience to imagine themselves performing that action, which in turn enhances persuasiveness (388). Moreover, as a person imagines themselves performing a specific action, their perceived ability to engage with that specific behaviour (i.e. self-efficacy) might be enhanced, and in turn this would increase actual adherence (388).

